	
 i. Progressive splenomegaly that is defined by the appearance of a previously absent splenomegaly that is palpable at greater than 5 cm below the left costal margin or a minimum 100% increase in palpable distance for baseline splenomegaly of 5-10 cm or a minimum 50% increase in palpable distance for baseline splenomegaly of greater than 10 cm. ii. Leukemic transformation confirmed by a bone marrow blast count of at least 20%. iii. An increase in peripheral blood blast percentage of at least 20% that lasts for at least 8 weeks.
5. Stable disease (SD)	None of the above.
6. Relapse	Loss of CR, PR, or CI. In other words, a patient with CR or PR is considered to have undergone relapse when he or she no longer fulfills the criteria for even CI. However, changes from either CR to PR or CR/PR to CI should be documented and reported.

4.2 Definition of end of the study

Patients may continue treatment until they progress, withdraw consent, experience unacceptable toxicity, start new MF therapy, and/or it is believed by the investigator to be in the best interest of the patient to discontinue. The study will continue until the last patient completes all required safety evaluations per extension phase of protocol. Data on patients will continue to be collected on all patients who remain on study.

4.3 Timing of interim analyses and design adaptations

No interim analyses are planned for this study.

4.4 Early study termination

The sponsor/investigator has the right to terminate the study at any time. Should this be necessary, the patient should be informed, and seen as soon as possible to perform a final visit. At this visit, the same assessments should be performed as End of Treatment, see Appendix A. The investigator will be responsible for informing the patients and the IRBs and/or ECs and FDA, as well as other relevant committees at MSSM of the early termination of the trial.

5 Population

5.1 Patient population

Adult male or female patients ages 18 or older, who have been diagnosed with Primary myelofibrosis (PMF), Post-polycythemia vera related myelofibrosis (Post PV MF) or Post Essential Thrombocythemia related Myelofibrosis (Post ET MF) as defined by the World Health Organization (WHO 2008), will be included in this study. These patients will be seen at the Mount Sinai School of Medicine Myeloproliferative Disorders Program.

Patients must be classified by the International Working Group for Myelofibrosis Research and Treatment (IWG-MRT) (Passamonti, 2010) and be either Intermediate-2: 3-4 points; or High Risk: 5 or more points. Patients can have either chronic phase (MF-CP), or accelerated phase (MF-AP) disease.

Patients may have received prior therapy for MF, but must discontinue chemotherapy for 3 weeks (except for hydroxyurea which can be discontinued 24 hours before starting RUXOLITINIB), and targeted therapy for 2 weeks prior to screening. Anagrelide can be continued up until 24 hours of starting the RUXOLITINIB. An exception are patients currently on at least 10mg BID of RUXOLITINIB for greater than 3 months and who have not shown an optimal response (i.e. without 50% reduction in palpable splenomegaly or 50% reduction in symptom burden). With a reduction of RUXOLITINIB to 10mg BID these patients may enter onto the study without stopping RUXOLITINIB. This trial will allow

patients who were treated with either HDACi's or JAK2 inhibitors, as long as these agents were not discontinued due to clinically relevant toxicities per the investigator.

Patients enrolled in this study are not permitted to participate in additional parallel investigational drug or device studies.

The investigator or designee must ensure that only patients who meet all the following inclusion and none of the exclusion criteria are allowed to enter study treatment in this study. Written informed consent must be obtained prior to any screening procedures.

5.2 Inclusion criteria

- 1 Male or female patients aged \geq 18 years old
- 2 Ability to provide written informed consent obtained prior to participation in the study and any related procedures being performed
- 3 Intermediate-2 and higher by IWG-MRT Post PV/ET MF and PMF patients either in
 - a. Chronic Phase (MF-CP)
 - b. Accelerated Phase (MF-AP)
- 4 Patients must meet the following laboratory criteria:
 - a. ANC \geq $.750 \times 10^9/L$
 - b. Platelets $\geq 75 \times 10^9/L$
 - c. Creatinine $\leq 1.5 \times$ ULN,
 - d. AST and ALT $\leq 2.5 \times$ ULN
 - e. Serum bilirubin $\leq 1.5 \times$ ULN (unless Gilbert's syndrome and evidence of hemolysis)
 - f. Serum potassium \geq LLN
 - g. Total serum calcium [corrected for serum albumin] or ionized calcium \geq LLN,
 - h. Serum magnesium \geq LLN
 - i. Serum phosphorus \geq LLN
 - j. Free T4 within normal limits
- 5 ECOG Performance Status of ≤ 3
- 6 Any prior therapy with JAK2-TKI, hypomethylating agents, HDACI, mTORi, or iMiDs is allowed as long as it is greater than 3 weeks since last dose of administration and in the case of a JAK2-TKI or HDACI that discontinuation was not due to non-hematologic drug toxicity. An exception to this criteria are patients currently on at least 10mg BID of ruxolitinib for greater than 3 months and who have not shown an optimal response (i.e. without 50% reduction in palpable splenomegaly or 50% reduction in symptom burden). With a reduction of ruxolitinib to 10mg BID these patients may enter onto the study without stopping ruxolitinib.

Exclusion criteria

1. Patients who will need valproic acid for any medical condition during the study or within 5 days prior to first PANOBINOSTAT treatment.
2. Impaired cardiac function or clinically significant cardiac diseases, including any one of the following:
 - a. With permanent cardiac pacemaker

- b. Resting bradycardia defined as <50 beats per minute
- c. QTcF >480 msec on screening ECG
- d. Complete Left bundle branch block, bifascicular block
- e. Any clinically significant ST segment and/or T-wave abnormalities
- f. Presence of unstable atrial fibrillation (ventricular response rate >100 bpm).
Patients with stable atrial fibrillation can be enrolled provided they do not meet other cardiac exclusion criteria.
- g. Symptomatic congestive heart failure (NYHA class III-IV)

3. Impairment of GI function or GI disease that may significantly alter the absorption of PANOBINOSTAT or RUXOLITINIB
4. Other concurrent severe and/or uncontrolled medical conditions (e.g., uncontrolled diabetes or active or uncontrolled infection) including abnormal laboratory values, that could cause unacceptable safety risks or compromise compliance with the protocol
5. Patients using medications that have a relative risk of prolonging the QT interval or inducing torsade de pointes if treatment cannot be discontinued or switched to a different medication prior to starting study drug
6. Concomitant use of strong CYP3A4 inhibitors
7. Patients who have received targeted agents within 2 weeks or within 5 half-lives of the agent and active metabolites (whichever is longer) and who have not recovered from side effects of those therapies.
8. Chemotherapy within 3 weeks prior to screening are excluded (other than hydroxyurea at stable doses and will be discontinued 24 hours prior to starting study drug).
9. Patients with an active bleeding tendency or are receiving any treatment with therapeutic doses of sodium warfarin (Coumadin[®]) or coumadin derivatives. Patients will be allowed to enter study on aspirin at doses of 81mg/d.
10. Patients who have undergone major surgery≤ 4 weeks prior to starting study drug or who have not recovered from side effects of such therapy
11. Women who are pregnant or breast-feeding or women of childbearing potential (WOCBP) not using an effective method of birth control. WOCBP are defined as sexually mature women who have not undergone a hysterectomy or who have not been naturally postmenopausal for at least 12 consecutive months (i.e., who has had menses any time in the preceding 12 consecutive months). Women of childbearing potential must have a negative serum pregnancy test within 24hrs of receiving the first dose of study medication.
12. Male patients whose sexual partners are WOCBP not using effective birth control
13. Patients with a prior malignancy within the last 5 years (except for basal or squamous cell carcinoma, or *in situ* cancer of the cervix)
14. Disease associated with secondary MF such as metastatic carcinoma, lymphoma, myelodysplasia, hairy cell leukemia, mast cell disease or acute leukemia (including M7 disease or acute panmyelosis with MF)

6 Treatment

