At 24 weeks, 41.9% of patients treated with ruxolitinib experienced a 35% or greater reduction in spleen volume compared to 0.7% of patients receiving placebo ($P < 0.0001$). 45.9% of ruxolitinib treated patients regardless of their JAK2 mutational status experienced a $\geq 50\%$ improvement in constitutional symptoms as compared to 0.7% in the placebo group. Survival analysis on extended ruxolitinib therapy with a mean follow up of 52 weeks showed a statistically significant reduction in death with a hazard ratio of 0.499 (0.254, 0.98) and a probability of survival compared to placebo of 0.98 vs 0.90 and 0.84 vs 0.77 in patients with a baseline hemoglobin $>10\text{g/dL}$ and $<10\text{g/dL}$, respectively (27). In further subset analysis, patient age ≤ 65 years appeared to have a survival benefit over > 65 years of age with a HR 0.22 (0.06,0.84) with ruxolitinib therapy.

The drug therapy was uniformly ineffective in reversing histopathological abnormalities in the peripheral blood or marrow, eliminating marker cytogenetic abnormalities or reducing the

JAK2V617F allele burden to a degree associated with tyrosine kinase inhibitor therapy of BCR/ABL1 for chronic myeloid leukemia. The other limitation of the agent that has been the rapid return of splenomegaly following discontinuation of the drug and the occasional occurrence of life threatening syndromes attributed to the rapid elevation of cytokines. This “ruxolitinib withdrawal syndrome” has been described in 5 of the 47 MF patients treated at Mayo Clinic that had rapid discontinuation and the authors advise tapering the drug when possible in addition to upfront discussion with the patient regarding this potential drug associated serious adverse event (28).

The *COntrolled Myelofibrosis Study with ORal JAK2 inhibitor Treatment COMFORT-2* study was a randomized (2:1), Novartis sponsored, open-label phase III clinical trial conducted in nine European countries comparing ruxolitinib to best available therapy (BAT) (29). Hydroxyurea (46.6%), steroids (16.4%) and supportive therapy (32.9%) comprised the BAT arm. At a median age of 66 years, 219 patients with intermediate-2 or high risk MF were randomized (146 ruxolitinib, 73 BAT).

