At this time there still exists no standard medical treatment for myelofibrosis and of the many drugs that have been used in the past (hydroxyurea, melphalan, danazol, interferon-alfa, thalidomide, lenalidomide) and presently being investigated (JAK2-TKI, HDACI, mTORi pomalidomide) have not been shown to affect the natural history and progression of disease. These drugs have individually shown the ability to induce response rates as measured in spleen reduction, amelioration of constitutional symptoms and to some degree modulation of hematologic profile and reduction in JAK2V617F allele burden. We believe that the combination of the RUXOLITINIB and PANOBINOSTAT is a novel and rational approach to the treatment of MF based on both pre-clinical science and clinical data as single agents in MF.

To further the benefit seen with RUXOLITINIB in patients with MF, PANOBINOSTAT will be added to the treatment regimen to act synergistically in the blockade of the dysregulated pathway driving this disease. See Section 2.4 for more information on the preclinical study demonstrating the synergistic activity exerted by the combination of PANOBINOSTAT and the JAK inhibitor TG101209 against CD34⁺ primary MPN cells and JAK2V617F-expressing cell lines. This synergy will hopefully provide enhanced anti-proliferative activity in patients and reduce overall treatment related toxicity by using lower than single agent maximum tolerated dose levels. This clinical trial will be a single arm, safety and dose-finding phase I/II study, with a primary endpoint within the phase II portion of IWG-MRT treatment response and secondary endpoints of spleen volume response and changes in exploratory biomarkers

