10.4.2.2 Dose expansion

The cohort of 6 patients at the MTD and/or RPTD will be expanded by an additional 16 patients in order to further assess safety and tolerability. Thus the number of patients treated at the MTD and/or RPTD will be 22, which ensures that there is a 90% chance to detect any AE with a 10% incidence rate among patients treated at the MTD and/or RPTD. During this phase of the study, further defining of the biological activity of this combination will be explored. The primary endpoint of this portion of the trial is response rate by IWG-MRT criteria. We hypothesize a response rate of >40% in treated patients at C6D28 will constitute a positive primary endpoint. A positive response by IWG-MRT criteria includes SD, CI, PR, or CR. Since preclinical studies suggest a synergistic effect of the two agents in combination, we would expect a spleen response rate (>35% reduction in spleen volume by MRI or >50% reduction in palpable spleen) of >30% as was assumed in the COMFORT study. Since the proportion of patients obtaining this efficacy endpoint was 42%, we will have a target response for this secondary endpoint of >50%, and this will be reported in a descriptive manner.

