10.6 Exploratory objectives

The following exploratory efficacy objectives will be included on the study:

10.6.1 To assess preliminary efficacy of the combination of RUXOLITINIB and PANOBINOSTAT by physician palpation in all dosing cohorts

Spleen measurements by palpation will be obtained with a primary emphasis on the change in measurements from baseline to Week 12. Descriptive statistics will be provided for the spleen length and percent change from baseline over time. The proportions of patients with at least a 50% reduction in palpable spleen length at any time point, at week 12 and at week 24 will be summarized. This analysis will be done separately on patients in every dosing cohort, as well as, on the pooled patients, in the escalation phase.

10.6.2 To assess the preliminary efficacy at the MTD and/or RPTD by the use of MRI/CT

The endpoint for this objective will be the volumetric reduction in spleen size from baseline to Week 12 (or end of study, whichever comes early), as assessed by MRI/CT. The analysis will be restricted to patients in the expansion phase, who are dosed at the MTD and/or RPTD. Responders (defined as those achieving at least 35% reduction in splenic volume (compared to baseline), at week 12 or end of study, whichever comes first), will be summarized in terms of percentage rates of response, along with 95% confidence intervals. An **exact binomial confidence interval** (implemented using SAS procedure FREQ with EXACT statement for one-way tables) will be calculated (Clopper 1934). Descriptive statistics for the volumetric reduction in spleen size and percent change (from baseline) at the end of week 24 will also be provided. Since preclinical studies suggest a synergistic effect of the two agents in combination, we would expect a spleen response rate (>35% reduction in spleen volume by MRI) of >30% as was assumed in the COMFORT study. Since the proportion of patients obtaining this efficacy endpoint was 42% in COMFORT-1, we will have a target response for this secondary endpoint of >50%, and this will be reported in a descriptive manner.

10.6.3 To assess (preliminary) efficacy of the combination of RUXOLITINIB and PANOBINOSTAT by bone marrow biopsy in all dosing cohorts

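### The pooled spleen response rate cannot be read against the COMFORT-1-derived >50% target, because patients already on ruxolitinib with a suboptimal response are pooled with patients starting it

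*Combined protocol and SAP*

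**What the plan says.** **Who enters.** Under section 5.2 item 6, prior JAK2-inhibitor therapy "is allowed as long as it is greater than 3 weeks since last dose of administration". It then adds: "An exception to this criteria are patients currently on at least 10mg BID of ruxolitinib for greater than 3 months" whose response was not optimal, that is, "without 50% reduction in palpable splenomegaly or 50% reduction in symptom burden". For them: "With a reduction of ruxolitinib to 10mg BID these patients may enter onto the study without stopping ruxolitinib". Section 5.1 repeats the exception. The synopsis does not: it requires every drug used for MF to be stopped at least 28 days or 5 half-lives before study drug.

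**How spleen response is measured.** Section 7.2.2.3 takes the imaging baseline at screening, before the 28-day ruxolitinib induction. Section 7.2.2.1 measures palpation response from Cycle 1 Day 1, after induction.

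**The target.** Section 10.4.2.2 expects a spleen response above 30%, then says "we will have a target response for this secondary endpoint of >50" percent, to be reported descriptively. Section 10.6.2 gives the reason: "the proportion of patients obtaining this efficacy endpoint was 42% in COMFORT-1". Section 1.3.3 gives the source, a 24-week result from a placebo-controlled trial: "41.9% of patients treated with ruxolitinib experienced a 35% or greater reduction in spleen volume".

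**The analysis.** Section 10.6.2 plans one response rate with one exact 95% confidence interval for the expansion patients. Section 10.6.1 splits palpation results by dosing cohort only. Section 10.2 groups baseline summaries by initial dose and study phase. Nothing in section 10 caps, stratifies or tabulates by ruxolitinib exposure at entry.

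**The concern.** In a patient not on ruxolitinib at screening, the change in spleen volume contains the ruxolitinib response plus whatever panobinostat adds. In a current user, the shrinkage already obtained is built into the baseline, and the patient was selected for an inadequate response. The two groups have different expected response rates even if panobinostat does exactly the same in both.

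The 42% describes patients randomised to begin ruxolitinib. Raising it to more than 50% makes sense as a bar for ruxolitinib plus something useful in comparable patients. Current users are not comparable, and their share is left to recruitment.

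Section 2.1 gives the motive for the combination: "To further the benefit seen with RUXOLITINIB in patients with MF, PANOBINOSTAT will be added to the treatment regimen". A rate that mixes the two groups cannot be read as evidence for or against that added benefit. A cohort with many current users could fall short of 50% although panobinostat helps.

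**Working it through.** **Inputs from the documents.** 22 patients at the MTD/RPTD (section 10.4.2.2); target >50%, so at least 12 of 22 (11 of 22 is exactly 50%); reference rate 42% (section 10.6.2).

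**Inputs that are assumptions.** The number of current users, k, and the response rate in each group are not in the documents. I show ranges.

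**The plan's own figure.** The 22 is justified by adverse-event detection: 1 − 0.90^22 = 0.90, which reproduces the stated 90%. It says nothing about the spleen endpoint, for which section 10.8 states that no power analysis was done.

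**Step 1: reference.** If panobinostat adds nothing and all 22 are starting ruxolitinib, X ~ Binomial(22, 0.42) and P(X ≥ 12) = 0.16.

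**Step 2: effect of the mix.** Let X be the sum of Binomial(22 − k, 0.55) for patients not on ruxolitinib and Binomial(k, p) for current users, with p from 0.10 to 0.40. The expected rate is [(22 − k) × 0.55 + k × p]/22, and P(X ≥ 12) comes from the exact convolution.

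| Current users k | Expected pooled rate | P(at least 12 of 22) |
|---|---|---|
| 0 | 55% | 0.60 |
| 4 | 47–52% | 0.29–0.50 |
| 11 | 32.5–47.5% | 0.01–0.32 |

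For example, k = 11 and p = 0.10 gives (11 × 0.55 + 11 × 0.10)/22 = 0.325.

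**Step 3: confounding.** Assume rates without panobinostat of 42% in starters and 5% in current users, and a common benefit d added to both.

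| Benefit d | k = 0 | k = 11 |
|---|---|---|
| 0 points | 42% | 23.5% |
| 10 points | 52% | 33.5% |
| 20 points | 62% | 43.5% |
| 30 points | 72% | 53.5% |

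A 20-point benefit in a half-and-half cohort gives (11 × 0.62 + 11 × 0.25)/22 = 43.5% and P(at least 12 of 22) = 0.18. No benefit in a cohort of starters gives 42% and 0.16. The pooled rate hardly distinguishes these two situations. Within either column, however, the rate rises one for one with d, so panobinostat still drives the result once the mix is fixed.

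**The case against.** Several points on the other side stand.

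- **Nothing formally passes or fails.** The spleen target is descriptive, section 10.8 rules out formal testing of secondary variables, and the phase II primary endpoint is IWG-MRT response of stable disease or better. No go/no-go rule rests on the spleen rate.
- **The mix does not replace the drug effect.** A reader might infer that the spleen result depends on enrolment rather than on panobinostat. Step 3 shows that it depends on both.
- **Current users do not isolate panobinostat.** That inference is also tempting, but a user above 10 mg BID is reduced at entry, so the later spleen change mixes panobinostat with a ruxolitinib dose change. Section 4.1 ties the induction dose to the cohort's combination dose, which is 15 mg BID from cohort 4a on (Table 6-2), so the dose could also move the other way. The entry condition joins spleen and symptoms with "or"; on one reading, some current users already had a good spleen response.
- **Palpation is less affected.** Its baseline follows 28 days of ruxolitinib in every patient, which removes the first month of the difference, though not the rest.
- **Isolating panobinostat is not a stated objective.** The objectives are safety, a phase II dose and response to the combination; the passage on adding benefit is rationale.

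A reader might also extend the argument to dose-limiting toxicities or IWG-MRT response. The documents do not support that here: neither is judged against the 42%, stable disease counts as IWG-MRT success, and cohorts of 3–6 are too small to split.

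These points limit the severity. They do not answer the remaining fault: a pre-stated target will be set beside a rate from patients to whom part of it does not apply.

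**Conclusion.** The point holds as one of interpretation. The pooled spleen rate cannot be compared meaningfully with the >50% target, because enrolment mix and panobinostat effect are confounded. The likely direction is dilution, so a missed signal is the main risk rather than a false success.

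The size depends on the number of current users. With none, the problem disappears. Under the assumed rates, the chance of reaching the target falls from 0.60 to 0.29–0.50 with 4 current users and to 0.01–0.32 with 11. These figures illustrate sensitivity and do not forecast the trial. They take all 22 patients as the denominator, although section 10.6.2 could be read as the expansion patients only, and they take the COMFORT-1 ruxolitinib arm as patients starting the drug.

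The change is worth making because it is cheap, but it does not touch the primary endpoint or dose finding.

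**What to change.** In sections 10.4.2.2, 10.6.1 and 10.6.2:

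1. Report spleen response descriptively, with exact confidence intervals, by exposure at screening: current ruxolitinib user; previously exposed to ruxolitinib or another JAK2 inhibitor and off drug; naive. A simple on/off split is not enough, because item 6 also admits washed-out patients who may not be first-time starters.
2. Apply the COMFORT-based >50% target only to patients starting ruxolitinib for the first time. Show the pooled rate without that target.
3. State that current users' spleen change is also affected by the ruxolitinib dose change at entry, and that imaging and palpation use different baselines (screening and Cycle 1 Day 1).
4. Reconcile the synopsis requirement to stop all MF drugs with the exception in sections 5.1 and 5.2, and reconcile the exception's entry dose with the induction dose in section 4.1.

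No split of dose-limiting toxicities is needed.

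**Cost.** Items 1–3 are analysis wording; prior and current medication is already collected at screening (sections 7.1.2 and 7.1.2.3). Item 4 needs a protocol clarification. The price is precision: the exact 95% interval is 32–76% for 12 of 22, 26–74% for 9 of 18, and 7–93% for 2 of 4. The smallest group will support description only.
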